- Abbreviations: ALT: Alanine aminotransferase; AST: Aspartate aminotransferase; BID: twice per day; BUN: Blood urea nitrogen; CBCs: Complete blood counts; CD: Cluster of differentiation; CLL: Chronic lymphocytic leukemia; CR: Complete response; CT: Computerized tomography; ECG: Electrocardiogram; ECOG: Eastern Cooperative Oncology Group; EOT: End of treatment; FISH: Fluorescence *in situ* hybridization; F/U: Follow-up; LDH: Lactate dehydrogenase; MRI: Magnetic Resonance Imaging; PBMC: Peripheral blood mononuclear cell; PD: Progressive disease; PDL1: programmed death ligand-1; PE: Physical exam; PET: Positron emission tomography; PK: Pharmacokinetics; QTc: Corrected QT interval; RBC: Red blood cell; SAE: Serious adverse event; TLS: tumor lysis syndrome; WBC: White blood cell; WCBP: Women of child-bearing potential

Table 11: Schedule of Assessments (LAM-002A/Atezolizumab Combination Therapy)

				Cycle 1			Cyc	es ≥2	End of	Long-Term F/U
Assessment	Screening			Day			D	ay	Treatment (EOT)	
	-28 to -1	1	2	3	8	15	1	15-22		
Informed consent	X									
Inclusion/exclusion criteria	X	Xª								
Demographics	X									
Medical history	X									
Signs and symptoms, PE ^b	X	Xc					X		X	
ECOG performance Status	X	Xc					X		X	
Vital signs	X	X ^d			X ^d	X^d	X		X	
ECG	X	X ^d			X ^d	X^d	X		X	
HIV, HBV, and HCV serology	X									
Hematology ^{e, f}	X	X			X	X	X		X	
Serum chemistry ^{f, g}	X	X	$X^{\mathbf{f}}$	X^{f}	X	X	X		X	
Serum thyroid function ^h	X						X			
Coagulation	X									
Urinalysis ⁱ	X	Xc					X		X	
Pregnancy testing	X	X^{j}					X		X	
PET/CT or CT (or MRI) scans (based on	X ^k							X ^l	X ^m	
indication) for response assessment										
PK/PD sampling ⁿ		X			X	X				
Bone marrow aspirate/biopsy	X°							X ^p		
Biomarker – tumor tissue ^q	X									
Biomarker – plasma tumor DNA ^r		X				X			X	
Biomarker – plasma cytokines ^s		X			X	X	X		X	
Biomarker – PBMC/B cells ^t	X									
Biomarker – saliva ^u	X									
LAM-002A administration in clinic ^v		X			X	X				
Atezolizumab infusion ^w		X								
Adverse events						Throug	hout study			
Concomitant medications ^x			Throughout study							
Long-term F/U ^y										X

Protocol: LAM-002A-NHL-CLN01

- A Eligibility will be confirmed by C1D1.
- B Complete PE will be performed at Screening. A directed PE, including weight, will be performed within 72 hours prior to the start of each cycle and EOT.
- C Assessment/test does not need to be repeated on C1D1 if baseline was within normal limits and conducted within 72 hours of first dose.
- D Obtained on Day 1 for all cycles. For C1D1 and C1D8 obtained prior to dosing and 1 hour (± 15 minutes after dosing), 2 hours (± 30 minutes), 4 hours (± 1 hour), and 8 hours (± 1 hour) postdose. For C1D15, obtained prior to dosing.
- E Hematology includes hemoglobin, hematocrit, RBC count, platelet count, WBC and differential.
- F All hematology and chemistry laboratory parameters should be assessed at Screening, on C1D1, C1D8, C1D15, C≥2D1 (all subsequent cycles), and at EOT. Obtaining a chemistry laboratory parameter on C1D2 and C1D3 is only required in subjects with intermediate or high risk of TLS (per the risk definition in Section 6.8.1). Except for C1D1, C1D2, and C1D3, these parameters may be obtained within 72 hours prior to the planned day of collection.
- G Serum chemistry includes albumin, alkaline phosphatase, total bilirubin, BUN, calcium, carbon dioxide, chloride, creatinine, glucose, inorganic phosphorus, potassium, total protein, LDH, ALT, AST, sodium, and uric acid.
- H Serum thyroid function tests include TSH, free T3, and free T4 at C3D1, C5D1, C7D1, C9D1, and then every 4 cycles (12 weeks)...
- i Urinalysis includes appearance, specific gravity and pH as well as a semi-quantitative "dipstick" evaluation of glucose, protein, bilirubin, ketones, leukocytes, and blood. Microscopic examination of sediment will be performed if urinalysis is positive for WBC, proteins or blood. Urinalysis may be obtained within 72 hours prior to the planned day of collection.
- J Pregnancy testing (serum or urine) will be required for women of childbearing potential (WCBP) only. Testing is required at Screening; within 72 hours of Day 1 of each cycle and at EOT. Test does not need to be repeated on C1D1 if baseline was negative and conducted within 72 hours of first dose.
- K Imaging as appropriate for disease indication will be conducted within 30 days before C1D1. Suitable scans performed prior to Screening and within 30 days before first dose may be used for baseline tumor assessments.
- L Assessment of disease status will be conducted with standard imaging as appropriate for indication. During treatment, scans will be repeated for tumor assessment within 7 days before C3D1, C5D1, C7D1, C9D1, and then every 4 cycles (12 weeks) until PD or use of alternative antineoplastic therapy.
- M Imaging at EOT is not required if PD has already been radiographically documented or last imaging was within 4 weeks of EOT visit.
- N Blood sampling for determination of the plasma concentrations and activity of LAM-002A and metabolites will be performed on C1D1 and C1D8 as follows: pre-dose, 30 minutes, 1, 2, 4, 6, 8 hours post-first dose of the day. Sampling on C1D15 will be pre-dose only. Subjects are required to come to the study site in a fasting state prior to the collection of certain PK samples.
- O Bone marrow aspirates/biopsies performed within 2 months prior to first dose may be used for clinical baseline assessments. Baseline bone marrow biopsies/aspirates may be omitted if not deemed essential for response assessment or patient management and there is another source of tumor tissue for pretreatment evaluation of gene expression and prognosis.
- P If necessary per applicable response criteria, a repeat bone marrow biopsy or aspirate will be required for subjects who have a CR by imaging and PE.
- Q Fresh tumor tissue (preferred) or archival tissue from the most recent available biopsy or surgery (within 4 months prior to the start of screening) must be obtained pretreatment for nucleic acid extraction. For subjects undergoing a biopsy, adequate tumor tissue should be acquired via excisional biopsy, incisional biopsy or core needle biopsy (e.g., ≥ 3 passes using a 16-gauge core needle). Confirmation of tumor in biopsy with fine needle aspirate, touch prep, or FFPE processing is requested when possible. The tumor lesion selected should not have been previously irradiated and should not be an index lesion that is followed for response assessment. Alternatively, cells from a bone marrow aspirate may be obtained in subjects with bone marrow involvement due to NHL (≥50% of cells). Tissue will be submitted for evaluation of the percentage of tumor cells and analysis of genetic alterations and/or gene expression that may predict anti-lymphoma activity and/or pharmacodynamics activity. In addition, the fresh biopsy or tumor tissue from the most recently availably biopsy or surgery will be evaluated for known prognostic characteristics (e.g., for DLBCL: ABC or GCB subtype; expression of BCL2, BCL6, Ki-67, CD20, and MYC; other mutational status), for PDL1 status, and for immune infiltration. The baseline biopsy procedure (if required) should ideally be performed after the study candidate has undergone the baseline radiology examination and is otherwise considered eligible for study participation.

Protocol: LAM-002A-NHL-CLN01

Version 9, 18 Feb 2020

- R Plasma will be collected on C1D1 (predose), on C1D15 (predose), and at EOT visit for evaluation of circulating tumor DNA to measure tumor burden and mutational changes.
- S Plasma will be collected for evaluation of circulating cytokines (including IL-12 and IL-23) on C1D1 (predose), C1D8 (predose), C1D15 (predose), C2D1, and at EOT.
- T PBMCs/B-cells will be collected during Screening for determination of changes in gene expression that may predict or correlate with anti-lymphoma activity and/or pharmacodynamic activity and will also serve as normal-tissue controls for gene mutation studies in tumors.
- U Saliva will be obtained during Screening as a normal-tissue control for gene mutation studies in tumors.
- V LAM-002A to be administered to the subject in clinic (with recording of the date and actual clock time of the LAM-002A administration). On C1D1, LAM-002A will be started on a BID schedule after administration of premedications (see Section 6.8.3.1) and ~15 to 30 minutes prior to the start of the initial atezolizumab infusion. On C1D8, the morning dose of LAM-002A will be administered after premedications (see Section 6.8.3.1) and ~15 to 30 minutes prior to the atezolizumab infusion
- w Atezolizumab, 1200 mg, will be administered by intravenous infusion over ~30 minutes every 3 weeks.
- X Information on concomitant medications and other treatments will be collected from 14 days prior to informed consent through 30-37 days after the last dose of study drug.
- Y Subjects who have discontinued study treatment for reasons other than PD will be assessed at a minimum of every 12 weeks until documentation of PD, start of new anti-cancer therapy or for up to 1 year from the last enrolled subject's first treatment (C1D1) whichever comes first. Long-term follow-up survival information will be obtained in all surviving subjects who permanently discontinue study therapy. Such information may be collected at ~3- to 6-month intervals at the sponsor's discretion through 3 years. This long-term follow-up information will be gathered during routine clinic visits, other study site contact with the subjects, or via telephone or e-mail with the subjects/caregivers or referring physician offices.

Abbreviations: ALT: Alanine aminotransferase; AST: Aspartate aminotransferase; BID: twice per day; BUN: Blood urea nitrogen; CBCs: Complete blood counts; CD: Cluster of differentiation; CLL: Chronic lymphocytic leukemia; CR: Complete response; CT: Computerized tomography; ECG: Electrocardiogram; ECOG: Eastern Cooperative Oncology Group; EOT: End of treatment; FISH: Fluorescence *in situ* hybridization; F/U: Follow-up; LDH: Lactate dehydrogenase; MRI: Magnetic Resonance Imaging; PBMC: Peripheral blood mononuclear cell; PD: Progressive disease; PE: Physical exam; PET: Positron emission tomography; PK: Pharmacokinetics; QTc: Corrected QT interval; RBC: Red blood cell; SAE: Serious adverse event; T3: triiodothyronine; T4: thyroxine; TLS: tumor lysis syndrome; TSH: thyroid-stimulating hormone; WBC: White blood cell; WCBP: Women of child-bearing potential

Version 9, 18 Feb 2020

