4.1.4. Pharmacokinetics, Clinical Efficacy and Safety

4.1.4.1. Pharmacokinetics

In humans, apilimod is orally bioavailable, rapidly absorbed, and extensively metabolized. Pharmacokinetic studies revealed generally dose-dependent increases in both C_{max} and AUC. t_{max} following oral administration was 1 hour in the absence of food and 2 to 3 hours when taken with food; in normal healthy volunteers and subjects with psoriasis, t_{max} ranged from 2 to 4 hours. Approximately 90% or more of the absorbed drug was cleared from circulation within 8 to 10 hours following administration, after which any remaining drug was eliminated with a terminal half-life of 5 to 10 hours following administration on the first day, increasing to 12 to 21 hours on Day 14. These findings suggest that either daily (QD) or BID dosing regimens may be appropriate. A small food effect was observed but is not deemed to be clinically significant.

The 2 dosage forms (apilimod dimesylate and apilimod formulations) used to date in clinical trials are bioequivalent. The 50-mg dose of apilimod dimesylate provides the same amount of active ingredient as the previously used 35-mg capsule of apilimod. Similarly, a 100-mg dose of apilimod dimesylate is equivalent to 70 mg apilimod. Future studies will utilize apilimod dimesylate capsules (LAM-002A).

Version 9, 18 Feb 2020

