Individual subjects who initiated treatment at a total daily dose level at or below the lower of the currently established MTD or the RP2D and who have not experienced a DLT after ≥ 2 cycles of treatment may have the LAM-002A total daily dose escalated to the next higher dose level if both the principal investigator and the medical monitor agree that a dose escalation is medically warranted (e.g., for a subject with stable disease who is tolerating the current dose level of LAM-002A therapy). In such subjects, successive adjustments to progressively higher total daily dose levels can be made at intervals of ≥ 4 weeks with the condition that the escalated total daily dose level cannot exceed a LAM-002A dose of 150 mg BID when administered continuously or the lower of the currently established MTD or RP2D of LAM-002A when given intermittently.

In a subject who experiences a DLT precluding resumption of LAM-002A therapy during a cycle, a new cycle of treatment may begin at the later of Day 29 or when AEs or laboratory abnormalities related to LAM-002A have returned to baseline levels. If drug-related AEs or laboratory abnormalities precluding further administration of study drug are not resolved to

baseline by Day 29, week-by-week delays in initiating the new cycle of treatment should be instituted. When all drug-related AEs and laboratory abnormalities have returned to baseline, the next cycle of therapy can be initiated. Upon initiation of a new cycle of therapy, the prior cycle of therapy will be considered completed.

Investigators are to discuss modifications in the dosing regimen with the medical monitor. The appropriate clinic staff should dispense the LAM-002A for the new dose level or schedule and instruct the subject/caregiver about the change in the dosing regimen.

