6.9.7. Drugs Known to Prolong the OT Interval

In a thorough QTc study, apilimod dimesylate at doses of 50 mg and 150 mg was associated with repolarization findings in excess of those deemed negative by regulatory guidance. The magnitude of the change was modest (~8.5 msec), peaked at 4 hours and did not demonstrate a dose trend. Preliminary QTc observations in the ongoing study in patients with hematological malignancies suggest the potential for dose- and exposure dependent Grade 1 or 2 QT prolongation.

As a precaution, the clinical potential of LAM-002A to prolong the QT interval will be assessed in this study. Accordingly, co-administration of LAM-002A and known QT-prolonging drugs is to be minimized because use of such drugs might confound interpretation of QT data from the trial.

Based on these considerations, protocol candidates who require therapy with drugs known to prolong the QT interval (as listed in Table 16) should not be enrolled into the study. If medically justified, protocol candidates may be enrolled if such drugs can be discontinued or alternative drugs that do not affect QT can be substituted >7 days before the first dose of study drug.

After the subject is enrolled to the protocol, use of drugs known to prolong the QT interval should be minimized but is not prohibited if administration of such drug is necessary and the subject appears to be benefiting from protocol therapy.

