8.2.4. Electrocardiogram

A 12-lead ECG with subject resting for 5 minutes will be done at Screening. Additional ECGs will be conducted according to Table 8: Schedule of Assessments (LAM-002A Continuous Monotherapy Administration), Table 9: Schedule of Assessments (LAM-002A Intermittent Monotherapy Administration), Table 10: Schedule of Assessments (LAM-002A/Rituximab Combination Therapy), and Table 11: Schedule of Assessments (LAM-002A/Atezolizumab Combination Therapy) – in Section 8.7 and more often if clinically indicated. Parameters measured will include heart rate, PR, QRS, QT, and QTc intervals (calculated by the Fridericia correction formula. Bazett's correction is acceptable if institutional policy). See Section 12 for PK time points. The ECGs will be reviewed and signed by the investigator.

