8.7. Schedules of Assessments

 Table 8:
 Schedule of Assessments (LAM-002A Continuous Monotherapy Administration)

	G .		Cycle 1				Cycle 2		Cycle ≥ 3 Day		End of	Long- Term
Assessment	Screening	Day					Ι	Day			Treatment	
	-28 to -1	1	2	3	8	15	1	15-28	1	15-28	(EOT)	F/U
Informed consent	X											
Inclusion/exclusion criteria	X	Xª										
Demographics	X											
Medical history	X											
Signs and symptoms, PE ^b	X	Xc					X		X		X	
ECOG performance status	X	Xc					X		X		X	
Vital signs	X	X ^d			X ^d	X^d	X		X		X	
ECG	X	X^d			X ^d	X^d	X		X		X	
HIV, HBV, and HCV serology	X											
Hematology ^{e, f}	X	X			X	X	X		X		X	
Serum chemistry ^{f, g}	X	X	Xf	Xf	X	X	X		X		X	
Coagulation	X											
Urinalysis ^h	X	Xc					X		X		X	
Pregnancy testing ⁱ	X	Xi					X		X		X	
PET/CT or CT (or MRI) scans (based on	X ^j							X ^k		$X^{\mathbf{k}}$	X ^l	
indication) for response assessment												
CLL baseline assessments ^m	X											
PK/PD plasma sampling ⁿ		X			X	X						
Bone marrow aspirate/biopsy	X°							X ^p		Xp		
Biomarker – tumor tissue ^q	X											
Biomarker – plasma tumor DNA ^r		X				X					X	
Biomarker – plasma cytokines ^s		X			X	X					X	
Biomarker – PBMC/B cell ^t	X											
Biomarker – saliva ^u	X											
LAM-002A administration in clinic ^v		X			X	X						
Adverse events							Throu	ighout Study				
Concomitant medications ^w							Throu	ighout Study				
Long-term follow-up (F/U) ^x												X

Protocol: LAM-002A-NHL-CLN01

- A Eligibility will be confirmed by C1D1.
- B Complete physical examination (PE) will be performed at screening. A directed PE, including weight, will be performed within 72 hours prior to the start of each cycle and EOT.
- C Assessment/test does not need to be repeated on C1D1 if baseline was within normal limits and conducted within 72 hours of first dose.
- D Obtained on Day 1 for all cycles. For C1D1 and C1D8 obtained prior to dosing and 1 hour (± 15 minutes after dosing), 2 hours (± 30 minutes), 4 hours (± 1 hour), and 8 hours (± 1 hour) postdose. For C1D15, obtained prior to dosing.
- E Hematology includes hemoglobin, hematocrit, RBC count, platelet count, WBC and differential.

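### After Cycle 1 no scheduled ECG is timed to dose, including after a within-subject dose increase, so the 4-hour QT peak is not reliably sampled

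*Combined protocol and SAP*

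**What the plan says.** Section 6.9.7 reports that in the thorough QTc study the effect was about 8.5 msec and "peaked at 4 hours and did not demonstrate a dose trend". It adds that preliminary data from this trial point to low-grade prolongation that may rise with dose and exposure, and that "the clinical potential of LAM-002A to prolong the QT interval will be assessed in this study".

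The ECG schedule is in Section 8.7. Footnote D of Table 8 begins "Obtained on Day 1 for all cycles. For C1D1 and C1D8 obtained prior to dosing and 1 hour" and continues to 2 hours, then "4 hours (± 1 hour), and 8 hours (± 1 hour) postdose. For C1D15, obtained prior to dosing". Tables 10 and 11 follow the same pattern. Table 9 (intermittent regimen) moves the second profile to C1D10. In all four tables the ECG marks from Cycle 2 onward carry no footnote d. An ECG is also scheduled at End of Treatment, without a time, and Section 8.2.4 provides for ECGs as set out "in Section 8.7 and more often if clinically indicated".

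In-clinic dosing is marked in Cycle 1 only; Section 6.8.2.3 makes all other dosing self-administered. Under Section 6.8.2.5, a subject without a DLT after at least 2 cycles may move to a higher dose, and "successive adjustments to progressively higher total daily dose levels can be made at intervals of" at least 4 weeks. The ceiling is 150 mg BID for continuous dosing, or the lower of the MTD and RP2D for intermittent dosing. Neither that section nor Section 8.7 links an ECG to the increase.

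**The concern.** An ECG informs a QT question only if its time after dosing is known. The protocol locates the peak at 4 hours and samples it well in Cycle 1, but then stops fixing the time just when two things can change: exposure after repeated dosing, and the dose itself. Any increase above the starting dose falls after the last timed tracing by construction.

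Two things are at stake. First, a subject whose dose is raised has no scheduled tracing near the peak at the new dose. Second, any comparison of later-cycle QTc with the Cycle 1 profiles would set timed values against untimed ones, so a difference or its absence could reflect clock time as much as drug effect. The protocol holds an unresolved question, no dose trend in the thorough QTc study against a possible dose and exposure relation here, and peak-time tracings in escalated subjects would bear on it.

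**Working it through.** The plan states no alpha, power or standard deviation for a QT analysis, so there is no figure to reproduce. The check is a count, an illustration of chance capture, and a look at what a pre-dose tracing would show.

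**1. Count of scheduled tracings (Table 8, ECG row and footnote D)**

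| Visit | Tracings | Timed post-dose | At 4 h ± 1 h |
|---|---|---|---|
| C1D1 (pre, 1, 2, 4, 8 h) | 5 | 4 | 1 |
| C1D8 (pre, 1, 2, 4, 8 h) | 5 | 4 | 1 |
| C1D15 (pre-dose) | 1 | 0 | 0 |
| Cycle 1 total | 11 | 8 | 2 |
| Each cycle from Cycle 2 | 1 | 0 | 0 required |
| End of Treatment | 1 | 0 | 0 required |

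Tables 10 and 11 give the same Cycle 1 times. Table 9 has its two 4-hour tracings on C1D1 and C1D10.

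**2. Chance that an untimed tracing falls 3 to 5 hours after a dose**

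Assumption, not in the documents: the tracing time is uniform over L hours after the dose. Then p = 2/L, and the chance that at least one of k tracings falls in the window is 1 − (1 − p)^k.

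| k | L = 12 (p = 2/12 = 0.167) | L = 8 (p = 2/8 = 0.25) |
|---|---|---|
| 1 | 17% | 25% |
| 2 | 31% | 44% |
| 4 | 52% | 68% |
| 6 | 67% | 82% |

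If a site always records before the dose, or within 3 hours of it, the chance is 0% for every k. Tied to the window, every such tracing would fall there by design.

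**3. What a pre-dose tracing would show, if that is when it is taken**

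On continuous BID dosing it would be about 12 hours after the previous dose, at trough. On the intermittent regimen (3 days on, 4 days off, Section 6.8.2.3), Day 1 of a new 28-day cycle follows 4 drug-free days.

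Section 4.1.4.1 says that approximately "90% or more of the absorbed drug was cleared from circulation within 8 to 10 hours following administration", but the same sentence gives a terminal half-life of 5 to 10 hours on Day 1 and 12 to 21 hours on Day 14. With a 12-hour interval, the accumulation ratio of that terminal phase is 1/(1 − 2^(−12/t½)):
- t½ = 12 h: 1/(1 − 0.5) = 2.00
- t½ = 21 h: 1/(1 − 0.673) = 3.06

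A single-dose residual of 10% is therefore not a usable estimate of trough exposure from Cycle 2 on. The lengthening also means that Day 8, the last timed post-dose ECG on continuous dosing, may not represent later exposure.

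**4. Size of the possible dose step**

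Stage 2 starts at 125 mg BID (Section 6.1.2). Moving to the 150 mg BID ceiling gives 300/250 = 1.20, a 20% rise in daily dose. A Stage 1 subject who started at 100 mg BID and reached the ceiling would have 300/200 = 1.50, a 50% rise. In both cases the subject's scheduled 4-hour tracings are all at the starting dose.

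**The case against.** The strongest defence is that intensive timed ECGs in Cycle 1, followed by simple per-cycle safety tracings, is a coherent design. The Cycle 1 tracings fall on the days of the pharmacokinetic profiles, so exposure and QTc can be related. The 150 mg BID ceiling is itself Stage 1 Dose Level 2 (Table 3), and Section 4.1.4.3 shows that it has been given. The thorough QTc study included 150 mg. Section 14.7 lists ECG change as a safety measure but specifies no cross-cycle QTc comparison. All of this stands, and it limits the point.

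A reader might go further and infer any of the following, which the documents do not support:
- **That later ECGs cannot detect a QT effect.** An untimed tracing may fall near 4 hours by chance, and End of Treatment and clinically indicated ECGs also exist, though none is aimed at the peak.
- **That escalated exposure is never assessed.** It is assessed at dose level, in subjects who started at that dose.
- **That later QTc changes will shrink towards zero, or reflect 10% or less of the drug.** This needs every tracing to be pre-dose. Section 8.3.1 sets pre-dose sampling for laboratory tests, not ECGs, and the half-life figures above undercut the percentage.

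What the defence does not answer is the within-subject gap. Section 6.6 allows at most 12 subjects per Stage 1 cohort. Those who started at 150 mg BID were on monotherapy, so they do not stand in for escalated combination subjects.

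**Conclusion.** The point holds in limited form. After Cycle 1 the schedule requires no ECG at a known time after dosing, and none is linked to a dose increase. The later tracings are not designed to capture the 4-hour effect and cannot be relied on to do so. The gap concerns later-cycle exposure and subjects whose dose is raised, including those on combination therapy; it is not an absence of peak-time data at any permitted dose level.

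In size, it is 2 tracings at 4 hours in Cycle 1 against 0 required in any later cycle. The 17% to 25% chance of capture per tracing rests wholly on the uniform-timing assumption. The number of subjects escalated is not given, so the effect on the trial's QT conclusions cannot be quantified. This is a cheap improvement to an otherwise workable schedule, not an error that invalidates the Cycle 1 assessment.

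**What to change.** - In footnote D of Tables 8 to 11, time the already scheduled C2D1 ECG, and the first scheduled Day 1 ECG after any dose increase, to the protocol's existing 4 h ± 1 h post-dose window, and mark those cells accordingly.
- Record the clock times of the dose and of the ECG at those visits. Footnote V (Tables 8 to 11) already asks for the dose time when the drug is given in clinic.
- In Section 14.7, state that QTc change is summarised across cycles only at matched times after dose. Section 14.2 leaves detailed methods to the SAP; if the SAP already says this, a cross-reference is enough.

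Cost: no additional ECG. One or two existing visits per subject need either a home dose coordinated with the appointment, a clinic dose or a longer stay, plus two time fields. No dose or escalation rule changes.
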